## Section 6 - Specific Aims

### 6) Provide a statement of specific aims and hypotheses that serve as the basis for this protocol. Emphasize those aspects that justify the use of human subjects.

Aim 1. To investigate the efficacy of MBSR to improve health-related quality of life in PD. Hypotheses: PD patients who complete MBSR will demonstrate (Primary Hypothesis 1a) greater improvement in HRQoL from baseline to post-treatment compared to PD participants randomized to a duration- and frequency-matched psychoeducational/supportive care control group; and (Hypotheses 1b) better HRQoL at the 6- and 12-month follow-up evaluations.

Aim 2. To examine the efficacy of MBSR to improve cognition in PD.

Hypotheses: PD patients who complete MBSR will demonstrate (Hypothesis 2a) greater improvement in cognition from baseline to post-treatment compared to PD participants randomized to a duration- and frequency-matched psychoeducational/supportive care control group, and (Hypotheses 2b) better cognition at the 6- and 12-month follow-up evaluations.

Aim 3. To determine the efficacy of MBSR in reducing mood symptoms in PD.

Hypotheses: PD patients who complete MBSR will demonstrate (Hypothesis 3a) greater improvement in mood from baseline to post-treatment compared to PD participants randomized to a duration- and frequency-matched psychoeducational/supportive care control group, and (Hypotheses 3b) better mood at the 6- and 12-month follow-up evaluations.

Exploratory Aim: To examine the mediators and moderators of treatment response on HRQoL following MBSR in PD. As cognitive and mood symptoms are associated with poor HRQoL in PD, we hypothesize that HRQoL change will be mediated and/or moderated by changes in cognition and mood from pre- to post-intervention. We will test the possible moderation/mediation effects of non-motor and motor symptoms on HRQoL following MBSR at 8 weeks (post-treatment), and 6- and 12 months.

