## Section 7 - Background and Significance

### 7) Provide a succinct discussion of relevant background information to justify performing the proposed study.

Over 80,000 Veterans with Parkinson's disease (PD) currently obtain their medical care within the VA Healthcare System and the number of Veterans with PD is expected to increase in the near future. Health-Related Quality of Life (HRQoL) is severely compromised in those with PD and worsens as the disease progresses. Non-motor symptoms, particularly cognition and mood, which also progressively decline over the course of the disease, contribute to poor and worsening of HRQoL in PD. Interventions that target these symptoms and improve HRQoL are critically needed. Mindfulness-based Stress Reduction (MBSR) is a non-pharmacological intervention that has been shown to improve HRQoL as well as improve mood and attenuate cognitive decline in older adults with and without neurological disorders. Although preliminary evidence supports MBSR as a promising intervention for PD, there has yet to be a comprehensive randomized controlled trial (RCT) of MBSR in this population. Results from our pilot trial ( $n = 20$ ) demonstrated that PD participants who completed an 8-week MBSR program ( $n = 8$ ) evidenced an improvement in overall HRQoL ( $d' = 1.14$ ), cognition (executive function;  $d' = 1.6$ ), and mood (anxiety;  $d' = 1.1$ ) compared to PD participants in an active control condition (Psychoeducation/Supportive Care;  $n = 12$ ); the latter of whom experienced a worsening of symptoms. These findings provide convincing preliminary evidence of MBSR efficacy for PD. In the proposed RCT, we will determine the efficacy of MBSR to improve HRQoL, cognition, and mood in a larger PD sample as well as determine the longevity of the treatment response.

Findings from this study will provide critical information about the efficacy of MBSR for HRQoL, cognition, and mood in PD. Furthermore, results will provide essential data regarding the long-term benefits of MBSR for non-motor symptoms in PD and elucidate potential mediators/moderators of the treatment response. Ultimately, this study will test a potential efficacious treatment for PD that could be widely implemented and disseminated throughout the VA Healthcare System and beyond.

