### Data Analysis

Data will be primarily analyzed using linear and multivariable random effects modeling.

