## Section 9.11 Pictures and Audio/Video Recordings of Patients

**9.11) Describe the purpose of photographs (facial), or audio, or video recordings of patients. Describe whether the recordings will contain, or potentially contain, identifiers. *Note: use of photographs or recordings must be covered in the informed consent process and documented consent documents (e.g., consent form, information sheets, telephone screen scripts).***

All sessions of MBSR and Psychoeducation/ Supportive Care will be audiotaped and available for rating in order to ensure fidelity and integrity of the protocol administration. All first sessions and a random sample of 10% of the audiotapes for the MBSR intervention will be reviewed by supervisors. [name] will also aid in the fidelity checks for the Psychoeducation intervention. Group facilitators will be provided corrective feedback, if needed. The facilitator will monitor attendance and note individual level of participation. Audio recordings will be destroyed at the end of the study. Audio recordings transferred into a computer system will be assigned group numbers and will not be individually identifiable. The key that relates the group numbers to the individuals will be stored separately, protected by strong passwords, and accessible only by approved study personnel. Recording members refer to each other by first name only, to ensure that they remain unidentifiable. Credibility, expectancy, engagement, practice, and facilitator competency will be examined in analyses.

We will also be video recording some of the group sessions. If 100% of group members agree to be recorded, we may video-record their group. If some of the subjects decline to be videotaped then we will not proceed with recording their session. Study participants may agree to such voluntary recording, or not, without any effect on the rest of their participation in the study.

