For all participants in this study, no exclusions will be made based on gender, race or ethnic background. Demographics will be analyzed for each group; should differences be apparent, these variables will be used as covariates in the analyses. As Veterans are mostly male and non-Hispanic white, non-Veterans recruited in order to increase our enrollment of females and ethnic minorities. This is necessary to closely match the prevalence of females (39%) and ethnic minorities (29% Hispanic; 21% Asian, and 19% Black) within PD. We attempt to recruit as many veterans as possible.

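### The Exploratory Aim lets pre-to-post change in cognition and mood moderate HRQoL change, although Hypotheses 2a and 3a predict that MBSR alters those changes; moderators should be variables measured before randomisation.

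*Combined protocol and SAP*

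**What the plan says.** Section 6 states the Exploratory Aim as a study of what mediates and what moderates the HRQoL response to MBSR. Its hypothesis gives both roles to the same variables: "we hypothesize that HRQoL change will be mediated and/or moderated by changes in cognition and mood from pre- to post-intervention". The next sentence is broader and also merges the roles: "We will test the possible moderation/mediation effects of non-motor and motor symptoms on HRQoL following MBSR at 8 weeks", continuing to 6 and 12 months. It does not say which measurement serves which role.

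The same section predicts that treatment moves those variables. Aim 2 has "Hypothesis 2a) greater improvement in cognition from baseline to post-treatment compared to PD participants" in the control group, and Aim 3 has "Hypothesis 3a) greater improvement in mood from baseline to post-treatment compared to PD participants" in the control group. Section 7 reports pilot differences favouring MBSR of d' = 1.6 for executive function and d' = 1.1 for anxiety.

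Three other statements bear on the analysis:

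- Section 9, Data Analysis: "Data will be primarily analyzed using linear and multivariable random effects modeling". The Section 5 summary says the same.
- Section 9.11: "Credibility, expectancy, engagement, practice, and facilitator competency will be examined in analyses".
- Section 10, on demographics that differ between groups: "should differences be apparent, these variables will be used as covariates in the analyses".

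None of these limits moderators to values measured before randomisation or separates a moderation model from a mediation model.

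**The concern.** A moderator of a randomised treatment effect has to be something that treatment cannot alter. Only then does comparing the arms within its levels keep the protection of randomisation. Change in cognition or mood over the 8 weeks is, on the trial's own hypotheses, partly produced by the arm. Participants in the two arms who show the same mood change are not comparable groups: one change came with MBSR and the other with the control programme. An arm-by-change interaction therefore compares groups formed after randomisation. It cannot say for whom MBSR works, which is what a moderator analysis is meant to answer.

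At stake is the interpretation of an exploratory result. The protocol expects the trial to clarify mediators and moderators of response, and it envisages wide use of MBSR if it works. A result reported as moderation by mood change could not guide that use, because mood change is unknown when treatment is offered.

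**Working it through.** The plan gives no figure for this aim, so there is none to reproduce. The checks below ask how closely the proposed moderator is tied to arm, how far an arm-by-change interaction can mislead, and what the replacement can detect.

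**Inputs from the documents.** 40 per group analysed (Sections 5, 9 and 10); pilot d' = 1.14 (HRQoL), 1.6 (executive function) and 1.1 (anxiety) (Section 7); groups of 6 to 8 (Section 9). **Assumed, because the documents do not state them:** two-sided 5% level, 80% power, and the correlation and spread values below.

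**1. Link between arm and change score.** With equal arms, r = d/sqrt(d^2 + 4).

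- d = 1.1: 1.1/sqrt(5.21) = 0.48
- d = 1.6: 1.6/sqrt(6.56) = 0.62
- d = 0.5 (an assumed smaller effect): 0.5/sqrt(4.25) = 0.24

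For a variable fixed before randomisation the expected value is 0.

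**2. Arm-by-change interaction when nobody's HRQoL effect differs.** Let T be the arm, HRQoL change Y = Y0 + 1.14T and mood change M = M0 + T(1.1 + e), with var(Y0) = var(M0) = 1, corr(M0, Y0) = rho and var(e) = v. Every participant has the same HRQoL effect, so there is no true moderation. The slope of Y on M is rho in the control arm and rho/(1 + v) in the MBSR arm. The interaction is the difference, -rho*v/(1 + v); the pilot effects 1.14 and 1.1 cancel out. Rejection rates come from 5,000 simulated trials with 40 per arm.

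| Case (assumed) | rho | v | Interaction | Arm-by-change test rejects |
|---|---|---|---|---|
| Equal spread | any | 0 | 0 | 4.9-5.4% |
| Low | 0.2 | 0.25 | -0.2 x 0.25/1.25 = -0.040 | 5.8% |
| Central | 0.4 | 0.5 | -0.4 x 0.5/1.5 = -0.133 | 10.1% |
| Extreme | 0.6 | 1.0 | -0.6 x 1.0/2.0 = -0.300 | 41.6% |

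A treatment-by-baseline interaction rejected in 5.0-5.2% throughout.

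**3. A second set of assumptions.** Here change in M acts on HRQoL as a pure mediator, by the same rule in both arms (4,000 trials, 40 per arm). False interaction rates for d = 0.5, 1.1 and 1.6:

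- linear effect: 4%, 6%, 5%
- saturating effect: 9%, 31%, 70%
- linear effect, with an unmeasured common cause that acts on the change score in the control arm only: 40%, 41%, 40%

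A baseline covariate gave 4.4-5.4% in every case. In the linear case the interaction test behaves, but the arm coefficient at mean change is about 0 although the total effects are 0.31, 0.66 and 0.96. The model has adjusted away the effect that passes through the mediator.

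**4. What a pre-randomisation moderator can detect.** With residual SD and moderator SD both 1, the standard error of the slope difference is sqrt(2/37) = 0.232 on 76 df. Then:

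- detectable at 80% power: (1.99 + 0.85) x 0.232 = 0.66 (the large-sample version, 2.80 x sqrt(2/40), gives 0.63)
- 95% half-width: 1.99 x 0.232 = 0.46
- simulated power: 0.81 at 0.66, 0.57 at 0.5, 0.25 at 0.3

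None of these allows for clustering within the treatment groups.

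**The case against.** The best defence is that the plan never writes down an arm-by-change interaction. The hypothesis uses an and/or wording, change scores are legitimate mediators, and the second sentence of the aim is wide enough to admit baseline moderators. On this view the roles have merely not been separated, in an exploratory aim on which no decision rests. The numbers also show little certain harm: no bias under equal spread with a linear effect, about 10% false positives at the central assumption, and higher rates only under extra spread, curvature or one-arm confounding that the documents neither state nor imply. A treatment-by-mediator term is a normal part of many mediation models. Finally, the replacement analysis has low power.

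Much of this stands and sets the weight of the point. It does not remove it. The hypothesis names the pre-to-post changes themselves as possible moderators, and no other statement moves that role to pre-treatment variables. Followed as written, the aim tests a treatment response as a moderator.

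Several stronger readings are tempting but not supported:

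- A reader might infer that only baseline scores on the outcome scales may be moderators. Any variable fixed before randomisation qualifies, including age and sex.
- A reader might infer that a large false interaction is to be expected. Its size rests wholly on assumed values.
- A reader might infer that the mediation plan is also at fault because mediator and HRQoL are measured together at 8 weeks. That is a general limit of same-visit mediation, not an error peculiar to this plan.
- A reader might see a conflict in the motor assessments. The specific UPDRS-III sentences (baseline and 12 months) can be read as refining the general battery list.

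**Conclusion.** The point holds as a minor one. The Exploratory Aim allows variables that the trial expects MBSR to change to be treated as moderators of its effect. An interaction with such a variable does not identify who benefits from randomised treatment, whatever its size. This follows from Section 6 alone and needs no numerical assumption.

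Bias in the interaction is a possible further problem. It is zero under equal spread and a linear effect, and -0.04 to -0.30 over the assumed values of rho and v. The documents give no basis for choosing among these, so the range illustrates the problem and does not predict its size.

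A reader might infer that the trial's main conclusions are at risk. They are not: Primary Hypothesis 1a and Aims 2 and 3 compare the arms directly, and neither they nor the sample size depend on this analysis.

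**What to change.** Reword the Exploratory Aim so that each role has its own variables, for example: *Changes in cognition and mood over the intervention will be examined as mediators of HRQoL change. Moderators will be tested as treatment-by-covariate interactions using variables measured before randomisation (e.g. baseline cognition, mood, motor severity, age, sex), reported as estimates with 95% intervals.* Add that a treatment-by-mediator term may stay inside the mediation model but is not to be reported as moderation of the treatment effect.

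The cost is a change of wording. Cognition, mood and motor severity are already in the baseline assessment and demographics are already collected, so no visit, test or extra participant is needed. Section 9 places the battery about a week before the group starts and describes it ahead of randomisation, but does not state the order outright; the reworded aim should confirm it.

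The downside is precision. An interval of about +/-0.46 SD per SD, wider if clustering in groups of 6 to 8 matters, will rarely settle whether a moderator exists. That is why estimates with intervals are preferable to significance statements. The gain is a result that can be interpreted, not a more sensitive test.

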## Section 7 - Background and Significance

### 7) Provide a succinct discussion of relevant background information to justify performing the proposed study.

Over 80,000 Veterans with Parkinson's disease (PD) currently obtain their medical care within the VA Healthcare System and the number of Veterans with PD is expected to increase in the near future. Health-Related Quality of Life (HRQoL) is severely compromised in those with PD and worsens as the disease progresses. Non-motor symptoms, particularly cognition and mood, which also progressively decline over the course of the disease, contribute to poor and worsening of HRQoL in PD. Interventions that target these symptoms and improve HRQoL are critically needed. Mindfulness-based Stress Reduction (MBSR) is a non-pharmacological intervention that has been shown to improve HRQoL as well as improve mood and attenuate cognitive decline in older adults with and without neurological disorders. Although preliminary evidence supports MBSR as a promising intervention for PD, there has yet to be a comprehensive randomized controlled trial (RCT) of MBSR in this population. Results from our pilot trial ( $n = 20$ ) demonstrated that PD participants who completed an 8-week MBSR program ( $n = 8$ ) evidenced an improvement in overall HRQoL ( $d' = 1.14$ ), cognition (executive function;  $d' = 1.6$ ), and mood (anxiety;  $d' = 1.1$ ) compared to PD participants in an active control condition (Psychoeducation/Supportive Care;  $n = 12$ ); the latter of whom experienced a worsening of symptoms. These findings provide convincing preliminary evidence of MBSR efficacy for PD. In the proposed RCT, we will determine the efficacy of MBSR to improve HRQoL, cognition, and mood in a larger PD sample as well as determine the longevity of the treatment response.

Findings from this study will provide critical information about the efficacy of MBSR for HRQoL, cognition, and mood in PD. Furthermore, results will provide essential data regarding the long-term benefits of MBSR for non-motor symptoms in PD and elucidate potential mediators/moderators of the treatment response. Ultimately, this study will test a potential efficacious treatment for PD that could be widely implemented and disseminated throughout the VA Healthcare System and beyond.

## Section 9 - Design and Methods

**9) Describe the research design and the procedures to be used to accomplish the specific aims of the project. Provide a precise description of the planned data collection (include what systems or databases will be used/accessed to gather data), analysis and interpretation. For chart review studies, include the timeframe of collection. Address sample size, inclusion of women and minorities. Define in clear terms exactly what will be done to the human subjects.**

### **Participants**

Eighty eight participants (44 per group) with PD will be primarily recruited from the VA San Diego and secondarily from UCSD (please see recruitment section below for more information regarding recruitment strategy and sites) to ensure a final sample size of 80 (40 per group) after accounting for attrition.

#### Inclusion criteria:

- (1) Clinical diagnosis of Parkinson's disease based on the UK Brain Bank Criteria
- (2) >40 years of age
- (3) Able to walk or stand without dependence on assistive device
- (4) willingness to be audio-taped.

#### Exclusion criteria:

- (1) Secondary causes of Parkinsonism (e.g., corticobasal degeneration, progressive supranuclear palsy, drug-induced parkinsonism)
- (2) other neurological conditions (e.g., stroke)
- (3) clinical diagnosis of dementia based on any previous neuropsychological testing (pre-screening) or as indicated by neuropsychological testing (consented screening).
- (4) psychosis, antipsychotic treatment or treatment for substance abuse (within the past 30 days)
- (5) uncorrected vision or hearing to adequately participate in the intervention
- (6) Indication of wheel chair bound or bedridden unless aided
- (7) prior formal training in MBSR or regular current MBSR practice
- (8) active/current participation in a psychological/behavioral treatment, such as Cognitive Behavioral Therapy (CBT)
- (9) active/current suicidal ideation as indicated on item #9 of the Beck Depression Inventory (BDI-II;  $\geq 1$ ) and evaluation by a licensed clinician on the protocol.

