Potential subjects may also be recruited by a search of ICD codes for Parkinson's disease in CPRS. Any patients not previously referred to our study from VASDHS clinics aforementioned, who may be eligible for the study, will be notified via the uploaded Recruitment Letter that a research assistant on this protocol will be contacting them approximately 2 weeks from the day the letter is sent. A research assistant will then call the patient to explain the study and gauge interest in participating. If the patient indicates that they are not interested, the research assistant will thank them for their time and will not contact them again regarding the study. Similarly, potential subjects may be recruited from co-investigators' research studies previously completed (e.g., [name] or [name] research studies). If a research participant who is potentially eligible for our study indicated in the previously completed research study that they would like to be contacted for future research opportunities, he or she will be informed of our research opportunities via phone call by a research assistant. If the patient indicates that they are not interested, the research assistant will thank them for their time and will not contact them again regarding the study. If the subject continues to show interest in participating, he or she will be informed that they will be asked a series of screening questions to determine their potential eligibility for our study (see attached Phone Screen document).

All potential participants will call or meet with a member of the research team who will explain the study's purpose and answer any questions. If the individual expresses interest in the study, they will be administered an IRB-approved pre-consent telephone screen, which will inquire about the inclusion/exclusion criteria, including PD diagnosis, prior neuropsychological testing, cognitive/dementia diagnosis, and mobility to determine eligibility.

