### Section 11.1 Recruitment Materials

**11.1) Identify all recruitment materials (flyers, advertisements, letters, etc.) that will be used; include the web address for any web-based advertisements. The text of all communications with prospective participants must be reviewed and approved by the IRB before it can be used. You will be reminded to attach copies of recruitment materials to the initial submission packet. Note: Posting of flyers with pull tabs is not permitted within VASDHS (including the VMRF building). However, you may request to advertise on the e-boards (located at the elevators and throughout the facility) or on the VASDHS Research Opportunities web-page.**

Recruitment will take place mainly at the VA San Diego. Recruitment will also occur at associated clinics, UCSD, and within the San Diego community. Recruitment methods include:

1. Obtaining referrals through VA San Diego's Neurology and Neuropsychology Clinics
2. Handing out brochures
3. Posting electronic media advertisements
4. Participating in PD-related events, utilizing active support group, and medical professional contacts.
5. Attending various Parkinson's disease community events (i.e. Parkinson's disease walk, exercise classes, support groups)
6. Advertising via VASDHS Hospital TV monitors calling for potential research participants (please see attached VA monitor slide).
7. Advertise our study on appropriate online websites, such as the Michael J Fox Trial Finder (foxtrialfinder.michaeljfox.org). The same wording as the handouts will be used for these announcements.

Patients will also be recruited from other studies completed if they had indicated they would like to be contacted for future research opportunities.

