## Section 12.10 HIPAA Waivers and Alterations

**12.10a) Describe the purpose/nature of the HIPAA waiver or alteration and list specifically, what identifiers and health information are being requested under the waiver/alteration and identify whether the waiver is for access, use, and/or collection of this information.**

1) The waiver will be used to conduct a brief phone screen on potential patients referred to the

study from outside the VASDHS as referenced in section 9. The phone screen will be used to determine eligibility for the study so that potential participants do not waste time and unnecessary hardship traveling to the VASDHS. The study could not be practically conducted without the waiver and without access to and use of PHI.

The subjects will be screened via phone call to determine eligibility to participate. Contact information will also be collected to provide potential participants information on the study and follow-up with eligibility. The data that will be collected under the waiver will include:

- Name
- Mailing address
- Phone number(s)
- Veteran status
- Neurological diagnosis
- Age
- Gender

Immediate inclusion/exclusion questions include:

1. Do you have a history of a stroke?
2. Have you ever been diagnosed with any neurological condition (other than PD)?
3. Has your PD diagnosis been confirmed by a neurologist?
4. Do you have a history of Post Traumatic Stress Disorder (PTSD)?
5. Do you have any psychiatric or mental health diagnosis?
6. Any history of alcohol or substance abuse?
  - 6a. Do you currently use alcohol? Amount/frequency?
  - 6b. Current substance use? Amount/frequency?
  - 6c. Last time you consumed/used?
7. Do you have a history of memory problems or have you been diagnosed with dementia?
8. Have you ever had neuropsychological testing done before?
9. Any major changes in medications within the last month (or anticipated within the next month)?
10. Have you ever had surgical treatment for Parkinson's disease (i.e. DBS surgery)?
11. Do you have any vision, hearing or movement problems that could interfere with taking tests, reading, or interacting in a group setting?
12. Have you ever acquired a major head injury?
13. Are you able to walk unassisted or do you use an assistive device (i.e. cane, walking stick, wheelchair)?
14. Are you trained or currently participating in any Mindfulness Based Stress Reduction practice?

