15. Are you currently undergoing any psychological/behavioral interventions or therapies (i.e. Cognitive Behavioral Therapy)?
16. Do you have a history of a brain tumor?
17. Do you have a history of epilepsy or seizures?

2) The waiver will also be used to recruit potential study participants through the Neuropsychology, Neurology, and other relevant clinics at VASDHS. Patients who may be interested will be asked to sign a Research Candidate Form while at clinic, and a research assistant will contact them if they indicate on the form that they agree to be contacted. Additionally, the provider may inform the research team of a potential study participant. At that point, a research assistant will either go speak to the patient in person about the study if the patient expresses interest in meeting with study staff, or will send the patient a letter (uploaded in protocol documents) stating that we will be calling them about a research opportunity.

2b) The Research Candidate form asks for the patient's name, provider name, appointment day/time, and telephone number (if they indicate they would like to be contacted). Calling the subject will require patient's name and telephone number to later be contacted.

3) The waiver will also be used to reach potential study participants through CPRS (using the ICD codes for Parkinson's disease). For any patients who may be eligible, who were not previously referred to the research team by the clinician and did not sign a Research Candidate Form, will be sent a letter informing the patient that we will be calling them about a research opportunity. Sending a letter will require patient's name, mailing address, and telephone number to be contacted in the future.

3b) Recruiting by ICD code search requires knowing the patient's medical diagnoses (of Parkinson's disease). Sending the letter and making a follow-up phone call will require the patient's name, mailing address, and telephone number.

4) Finally, the waiver will also be used to reach potential study participants through previously completed research studies, if they had agreed to be contacted for future research opportunities. Any patients who may be eligible will be called to inform them of our new research opportunities.

This will require the patient's name, mailing address, and telephone number to be contacted in the future.

**12.10b) The proposed access, use, and/or disclosure of PHI involves no more than a minimal risk to the privacy of individuals.**

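### The eligibility criteria and phone screen bar prior MBSR training but not prior participation in the pilot's control programme, so former pilot controls are eligible as written (minor)

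*Combined protocol and SAP*

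**What the plan says.** The exclusion lists in Section 9 and Section 10 are identical here. Item (7) removes people with "prior formal training in MBSR or regular current MBSR practice". Item (8) removes those with "active/current participation in a psychological/behavioral treatment, such as Cognitive Behavioral Therapy (CBT"), which concerns treatment under way, not a programme finished in the past.

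The phone screen in Section 12.10 follows the same lines. Item 14 asks "Are you trained or currently participating in any Mindfulness Based Stress Reduction practice", and item 15 asks "Are you currently undergoing any psychological/behavioral interventions or therapies". No item asks whether the person has taken part in an earlier trial or in the control programme.

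Section 7 describes the team's own pilot of 20 people, in which 8 who completed MBSR were "compared to PD participants in an active control condition (Psychoeducation/Supportive Care"), the latter numbering 12.

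On recruitment, Section 11 states that "potential subjects may be recruited from co-investigators' research studies previously completed"; if the person had agreed to future contact, "he or she will be informed of our research opportunities via phone call by a research assistant". Section 11.1 is worded more broadly: "Patients will also be recruited from other studies completed if they had indicated they would like to be contacted for future research opportunities". Point 4 of Section 12.10 extends the HIPAA waiver to the same route.

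**The concern.** The criteria guard against prior exposure on one side of the comparison only. The pilot's MBSR completers are shut out by exclusion (7), while its control participants are not, although the new trial uses a control of the same name.

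Primary hypothesis 1a compares change in HRQoL between the arms. The HRQoL instrument listed in Section 9.8 is a self-completed questionnaire (PDQ-39), and mood is also measured by questionnaire. Blinding the examiner does not blind the person answering. Someone who has already sat through the control programme can tell which arm is the comparator. If assigned to it again, that person may meet similar material a second time. If assigned to MBSR, that person knows it is the other programme. Either could shift expectancy and self-report, and in different directions in the two arms.

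**Working it through.** **Is there a gap?** Take a person who completed the pilot's control programme, has never had MBSR training and is in no current therapy.

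| Check | Covers | Stops this person? |
|---|---|---|
| Exclusion (7), Sections 9 and 10 | MBSR training or practice | No |
| Exclusion (8), Sections 9 and 10 | Current treatment | No |
| Phone item 14, Section 12.10 | MBSR | No |
| Phone item 15, Section 12.10 | Current therapy | No |

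Phone item 8 asks about past neuropsychological testing and might bring pilot participation to light by chance, but no criterion would act on it.

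**Is there a route in?** The completed-studies route in Sections 11, 11.1 and 12.10 is worded widely enough to include the pilot, provided the person agreed to future contact. Clinic referral and the ICD-code search in Section 11 would not filter these people out either.

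**The plan's own sample size.** The target is 80 evaluable with 10% over-recruitment: 80 × 1.10 = 88, or 44 per arm, as stated. Dividing instead gives 80/0.90 = 88.9, rounded up to 89, so the stated figure is reproduced to within one person.

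**How many could be affected?** The inputs are 12 pilot controls (Section 7) and 88 enrolled (Section 9). Uptake is not given, so it is an assumption and is shown as a range. Share of sample = k/88. Expected number per arm under balanced allocation = k × 44/88 = k/2.

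| Re-enrolled, k | Share of 88 | Expected per arm |
|---|---|---|
| 0 | 0% | 0 |
| 3 | 3.4% | 1.5 |
| 6 | 6.8% | 3 |
| 9 | 10.2% | 4.5 |
| 12 | 13.6% | 6 |

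The last row is a ceiling. It needs every pilot control to be still eligible, reachable, willing and free of later MBSR training.

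**What cannot be computed.** The documents give no effect of prior control exposure on PDQ-39 or mood scores, so no bias in the treatment effect can be derived.

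**The case against.** The strongest reply is that the event may never occur. The pilot is not named as a recruitment source, and the completed-studies route is permissive, conditional on earlier agreement, and secondary to VA San Diego clinics and specialist referral. Section 9 offers MBSR to this trial's controls at the end of the study. If the pilot did the same, those who took it up are already excluded, but the documents do not say. All of this stands, and it is why the lower bound is 0.

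A second reply is that expectancy is already handled: the Credibility and Expectancy Questionnaire is listed in Section 9.8, and Section 9.11 says that credibility and expectancy will be examined. This stands in part. Measuring expectancy does not identify who has met the control programme before, so these people could not be separated out in an analysis.

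A third is that the asymmetry is defensible. MBSR is the skill under test, and Section 7 reports that pilot controls worsened, which suggests no lasting benefit to carry over. That answers carry-over but not recognition of the control arm. It is also fair that identical content is inferred from a shared name, so repetition is possible rather than established.

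Two stronger readings are tempting and should be resisted. A reader might infer that all 12 could land in one arm because whole groups are assigned, giving 12/44 = 27%. Groups hold about 6 to 8 people, so 12 cannot sit in one group, and group assignment does not by itself produce that outcome. A reader might also infer that overlap with the pilot undermines the trial because the evidence no longer comes from separate people. Nothing in the documents pools pilot and trial data, and overlap does not invalidate a randomised comparison.

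**Conclusion.** The gap is real, and the point is minor. As written, former participants in the pilot's control programme are eligible, and nothing at screening asks about them. Between 0 and 12 people are affected: at most 13.6% of the 88, with about 6 expected per arm at that ceiling under balanced allocation. The effect on expectancy and self-reported outcomes is plausible but unquantified. The conclusion rests on two readings: that the completed-studies wording is wide enough to include the pilot, and that the pilot's control resembles the one used here. The documents do not show that any pilot control has been or will be enrolled.

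**What to change.** Extend exclusion (7), in both Section 9 and Section 10, to prior participation in the pilot trial or its Psychoeducation/Supportive Care programme. Add the matching question beside item 14 of the phone screen in Section 12.10.

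The cost is one line in each list and one phone question. The downside is the loss of at most 12 potential recruits from the pool. The planned enrolment of 88 and the analysis do not change. If the sponsor prefers to keep these people eligible, the protocol should say so, record prior exposure at screening, and plan a sensitivity analysis without them.
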